# 9 STUDY POPULATION

Unless otherwise specified, all efficacy analyses will be performed on the ITT population and all safety analyses will be based on the Safety population. In the ITT population, the treatment assignment is based on the assignment upon randomization. In the Safety population, the treatment assignment is based on the actual treatment the subject received.

The comparability between the 2 treatment groups will be checked for demographic and baseline characteristics. The p-values from Fisher's exact test (for discrete variables) or Group t-test or Wilcoxon rank sum test (for continuous variables) will be included on summaries but are not intended to be used to test formal hypotheses. For these comparisons, missing or unknown values will be excluded from the calculations.

### 9.1 SUBJECT ACCOUNTABILITY

All subjects' disposition information will be listed by individual subject number, including the analysis population the subjects belong to, premature study drug discontinuation status, primary reason for premature study drug discontinuation, premature study discontinuation status, primary reason for premature study discontinuation, number of days on the study drug, and enrollment in the open label extension study (RIN-PH-202).

The listing of subject accountability will include the dates of informed consent and randomization, the first study drug dose, last study drug dose, and last assessment dates and times, and the last dose and assessment weeks. Whether subjects received the study drug, whether subjects completed the Weeks 4, 8, 12, 15, 16 assessments, and study discontinuation status will be summarized.

Information regarding whether each subject is included in each analysis population (see Section 6) will be listed. If a subject is not included in a particular analysis population, the reason for exclusion will be noted on the listing. Also noted on the listing will be the randomized treatment assignment and the actual treatment subjects have received. The summary will include the frequency and percentage of all subjects in each analysis population.

The stratification information used in the random assignment of subjects to treatment group (from the central randomization database) will be listed, including date and time of randomization and Baseline 6MWD category ( $\leq$ 350 meters versus >350 meters). Status of the treatment blind, and if broken, date/time of blind broken will be listed. The number of subjects in each stratum will be summarized by treatment group and overall.

# 9.2 **PROTOCOL DEVIATIONS**

The status of the entry criteria will be listed for all subjects. The listing will include the date of the initial screening assessment, whether all eligibility criteria were met (Yes/No), and a list of any specific entry criteria not met. This listing will also include the protocol version that the subject was enrolled under. Entry criteria violations will be summarized by treatment group and overall.

Additional protocol deviations will be documented throughout the study. All deviations will be reviewed by the clinical team prior to database lock and those that might affect subject safety or efficacy outcomes will be considered 'Major'. All other deviations will be classified as 'Minor'. Protocol deviations will be listed, including the date of the deviation, the type of deviation, the severity of the deviation (Major/Minor), and a description of the deviation. The protocol deviations will also be summarized by treatment group and overall.

### 9.3 OTHER DESCRIPTIONS OF STUDY POPULATION

### 9.3.1 Demographics

All demographic data will be listed for all subjects, including assessment date, date of birth, country, age, sex, ethnicity, race, weight, height, and body mass index (BMI). Age, age category (<65 years of age, 65 to <80 years of age, and ≥80 years of age), sex, ethnicity, race,

height, weight, and BMI will be summarized by treatment group and overall. The summary will include p-values (2-sided) from Fisher's exact test (for age category, sex, ethnicity, and race) and group t-test or Wilcoxon rank sum test (for age, weight, height, and BMI) comparing treatment groups.

# 9.3.2 Baseline Characteristics

Baseline characteristics will include the Baseline 6MWD, Baseline NT-proBNP, and hemodynamic parameters. Hemodynamic parameters, measured by the right heart catheterization (RHC), will include PVR, pulmonary artery pressure mean (PAPm), pulmonary capillary wedge pressure (PCWP), and details concerning vasodilator testing will be listed and summarized.

# 9.3.3 Medical History and PH-ILD History

All significant past or ongoing medical conditions will be listed for all subjects. The listing will include the Medical Dictionary for Regulatory Activities (MedDRA) system organ class (SOC) and preferred term (PT) for each condition listed, and whether the condition is ongoing at Randomization. These medical conditions will be summarized by PT within each SOC.

Information related to subjects' PH-ILD history will be listed. The listing will include the date of initial PH diagnosis, years since PH diagnosis, etiology of ILD (including IIP subcategory), date of confirmatory computed tomography (CT) scan, whether ILD diagnosis confirmed with a lung biopsy, and if so, the date of lung biopsy.

The current ILD diagnosis (ILD category) and IIP subcategory, time since PH diagnosis, and whether ILD diagnosis was confirmed via lung biopsy will be summarized by treatment group and overall. The summary will include p-values (2-sided) from Fisher's exact test (for current ILD diagnosis) or Wilcoxon rank sum test (for time since diagnosis) comparing treatment groups.

### 9.3.4 Concomitant Medications

All concomitant medications specified on the eCRF will be mapped to a standard name using the World Health Organization Drug Dictionary (WHO-DD).

The standard name and verbatim term of all concomitant medications will be listed for all subjects. This listing will include the date started (or indication that drug was ongoing at randomization), date discontinued (or indication that drug was ongoing at end of study), and the condition(s) treated/indication(s). If a subject received no medications, this will be indicated on the listing. Summary of concomitant medications present at Baseline and summary of concomitant medications added during the study will include the frequency and percentage of subjects in each treatment group receiving each drug (by coded standard name).

### **10 EFFICACY ANALYSES**

Except where otherwise noted, all efficacy analyses will only be performed on the ITT population (see Section 6).

# **10.1 PRIMARY EFFICACY MEASURES**

# 10.1.1 Primary Efficacy Analyses

# 10.1.1.1 Hypothesis

The primary efficacy endpoint of peak 6MWD assesses if inhaled treprostinil will increase the distance traversed in the peak 6MWT at Week 16 over placebo in subjects with PH-ILD. The null and alternative hypotheses are:

$$H_0: \mu_1 = \mu_2$$
$$H_a: \mu_1 \neq \mu_2,$$

where  $\mu_1$  and  $\mu_2$  are the median change from Baseline in 6MWD of the inhaled treprostinil and placebo treatment groups, respectively.

# 10.1.1.2 Primary Efficacy Analysis

All 6MWT data will be listed for all subjects. For each scheduled assessment, this listing will include the date test was performed (or date test was intended to be performed if subject is unable to attempt the test), start time of the test, nominal time point, last treatment dose, hours from last treatment dose to 6MWT start, if walk was attempted, total distance walked (in meters), whether subject received oxygen during the test, amount of supplemental oxygen, and any circumstances that adversely affected the walk (if any) including reason for not

attempting test (if any). The trough 6MWT measure will also be indicated. In addition, a listing of 6MWD with imputed values will be included for both peak and trough 6MWD data.

For the primary efficacy analysis, the effect of inhaled treprostinil versus placebo on change in peak 6MWD at Week 16 will be evaluated via analysis of covariance (ANCOVA). Change from Baseline in peak 6MWD is the dependent variable, and treatment and Baseline 6MWD are covariates in this ANCOVA model. Least squares means and standard errors for each treatment group, the least squares mean difference and its standard error, as well as a 95% confidence interval for the treatment group difference and p-value for treatment group comparison will be calculated from the ANCOVA model. This methodology will be carried out as follows:

- 1. Walk distances obtained after study drug termination or unblinding will be excluded (as described in Section 8).
- 2. Imputation rules in Table 8-1 will be applied.
- 3. The LOCF algorithm will be applied.
- ANCOVA will be conducted based on the pseudo SAS code: proc glm; class Treatment; model DistC = Treatment Dist0; run;

where DistC is the change from Baseline in peak 6MWD at Week 16 and Dist0 is the baseline measure of the 6MWD.

If the ANCOVA assumptions are violated, the primary efficacy analysis will be based on non-parametric analysis of covariance within the framework of the extended Cochran-Mantel-Haenszel test (Koch 1990, Koch 1998, Stokes 2000). Specifically, a Cochran-Mantel-Haenszel mean score test will be used on the standardized mid-ranks (ie, overall rank divided by the number of ranks +1, or "modified ridit" scores) of the residuals from an ordinary least squares regression with change from Baseline in peak 6MWD at Week 16 as a linear function of distance walked at Baseline (as a continuous variable). This methodology will be carried out as follows:

- 1. Walk distances obtained after study drug termination or unblinding will be excluded (as described in Section 8).
- 2. Imputation rules in Table 8-1 will be applied.
- 3. Calculate ranks. The pseudo SAS code is as follows:

proc rank nplus1 ties=mean out=ranks;

var DistC Dist0;

run;

where DistC is the change from Baseline in peak 6MWD at Week 16 and Dist0 is the baseline measure of the 6MWD.

4. Linear regression model will be fit using the rank values generated above. The pseudo SAS code is as follows:

proc reg data=ranks noprint;

model DistC=Dist0;

output out=residual r=resid;

run;

where DistC is the rank value of the change from Baseline in peak 6MWD at Week 16 and Dist0 is the rank value of the baseline measure of the 6MWD.

5. A mean score test, using the values of the residuals as scores, compares the treatment groups. Cochran-Mantel-Haenszel mean score statistic and p-value will be calculated, using the NOPRINT and CMH2 options in the TABLES statement of the FREQ procedure of SAS. The pseudo SAS code is as follows:

proc freq data=residual;

tables Treatment\*Resid / noprint cmh2;

run;

where Treatment indicates the randomized treatment group, and Resid represents the residuals obtained from the above linear regression models.

In addition to the p-value from the non-parametric method described above, the Wilcoxon

rank sum test and the Hodges-Lehmann estimate of median difference (as an estimate of

location shift between 2 treatment groups for the placebo-controlled treatment effect) will be

provided. The Wilcoxon rank sum test and the Hodges-Lehmann estimate can be obtained

through the following pseudo SAS code:

proc npar1 way hl Wilcoxon; class treatment; var DistC; run;

where DistC is the change from Baseline in peak 6MWD at Week 16.

# 10.1.1.3 Sensitivity and Subgroup Analyses

In order to analyze walk distances at each scheduled assessment, values for missing or excluded assessments up to and including Week 16 will be imputed according to rules described in Section 8.3.1.

To further support the robustness and assess the sensitivity of the primary efficacy analysis of change in peak 6MWD at Week 16 (provided that the primary analysis yields significant results), the above non-parametric and parametric analyses and summaries will be repeated using each of the following modifications (as data permit):

- The Per-protocol population will be used instead of the ITT population
- Missing data imputation using the LOCF method (based on peak values)
- Missing data imputation using the last rank carried forward (LRCF) method (based on peak values) (O'Brien 2005)
- Using only the observed values without imputation
- Including data collected after termination of the study drug
- ITT population excluding subjects with a reported exacerbation within 3 days of the Week 16 peak 6MWT measure
- Stratified by ILD etiology categories (IIP, CHP, Occupational, CPFE, and Other)
- Stratified by Baseline 6MWD categories (≤350 meters versus >350 meters, ≤median baseline 6MWD versus > median baseline 6MWD)
- Stratified by Baseline DLCO percent predicted (<40% versus  $\geq 40\%$ )
- Stratified by Baseline pulmonary vascular resistance (PVR) (<4 versus  $\geq 4$  WU)
- Stratified by sex (male versus female)
- Stratified by age group (<65 years of age, 65 to <80 years of age, and ≥80 years of age)
- Stratified by study drug dose at Week 16 (0 to 3 breaths, 4 to 6 breaths, 7 to 9 breaths, and 10 to 12 breaths).

A longitudinal data analysis using mixed model repeated measurement (MMRM) will also be performed to estimate the treatment difference in change in peak 6MWD at Week 16. The MMRM will include the change from Baseline in peak 6MWD as the dependent variable, treatment, week, and treatment by week interaction as fixed effects, and Baseline 6MWD as a covariate. An unstructured variance/covariance structure shared across treatment groups will be used to model the within-subject errors. An additional sensitivity analysis will be performed for percent change from Baseline to Week 16 in peak 6MWD using the same approach as the primary analysis method where the percent change from Baseline is calculated as

In addition, the impact of Baseline hemodynamics and Baseline PFTs, including PVR, PAPm, PCWP, FEV1, FVC, TLC, and DLCO as continuous variables, on peak 6MWD, will be explored using the regression approach.

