# 5 SAMPLE SIZE CONSIDERATIONS

Using an allocation ratio of 1:1 between inhaled treprostinil and placebo, a sample size of approximately 266 subjects (133 per treatment) would provide at least 90% power at a significance level of 0.05 (2-sided hypothesis) to detect a 30 meter between-treatment difference in the change from Baseline to Week 16 in 6MWD, assuming a standard deviation of 75 meters.

The total sample size will be approximately 314 subjects to account for a discontinuation rate of approximately 15%.

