### 8.2 EXAMINATION OF SUBGROUPS

For primary efficacy endpoints of change in 6MWD at Week 16, subgroup analyses will be performed. These subgroups will include:

- Etiology of ILD (Idiopathic Interstitial Pneumonia [IIP], Chronic Hypersensitivity Pneumonitis [CHP], Occupational, CPFE, Connective Tissue Disease [CTD], and Other)
- Baseline walk categories (≤350 meters versus >350 meters, ≤ median baseline 6MWD versus > median baseline 6MWD)
- ILD disease severity as measured by Baseline DLCO (<40% predicted versus ≥40% predicted)

- Sex (male versus female)
- Pulmonary Vascular Resistance (PVR) (<4 versus ≥4 Wood Units [WU])
- Age group (<65 years of age, 65 to <80 years of age, and  $\geq$ 80 years of age)
- Study drug dose at Week 16 (0 to 3 breaths, 4 to 6 breaths, 7 to 9 breaths, and 10 to 12 breaths)

No Type 1 error adjustments will be performed for these subgroup analyses.

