# **15.3 LIST OF FIGURES**

Figure Number	Figure Title
14.2.1	Mean Change from Baseline in Peak 6MWD (meter) by Visit
14.2.2	Mean Change from Baseline in Peak 6MWD (meter) at Week 16 by Inhaled Treprostinil Dose at Week 16
14.2.3	Forest Plot on Subgroup Analyses of Peak 6MWD (meter) at Week 16
14.2.4	Kaplan-Meier Plot of Time to Clinical Worsening Events

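### The subgroup plan repeats the primary treatment test within each level but never tests whether the effect differs between levels

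*SAP*

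**What the plan says.** SAP Section 8.2 names the subgroup factors for the primary endpoint and adds: "No Type 1 error adjustments will be performed for these subgroup analyses". Section 10.1.1.3, on sensitivity and subgroup analyses, states that, if the primary result is significant, "the above non-parametric and parametric analyses and summaries will be repeated using each of the following modifications". The modifications include a split by each factor.

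The analysis being repeated is that of Section 10.1.1.2. It gives least squares means, their difference with standard error and 95% confidence interval, and a p-value for treatment. The non-parametric version adds rank-based p-values. Section 15.1 lists a separate results table for each factor (14.2.1.10 to 14.2.1.16), and Section 15.3 lists a "Forest Plot on Subgroup Analyses of Peak 6MWD (meter) at Week 16".

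The only interaction term in the SAP is treatment by week, in the repeated-measures model. The regression on baseline hemodynamics and lung function at the end of Section 10.1.1.3 names no interaction with treatment. The protocol's analysis section has no such test either.

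The two factor lists differ. Section 8.2 gives six etiology levels. Section 10.1.1.3 gives five, without connective tissue disease.

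**The concern.** Significance in one level and non-significance in another is not evidence that the effect differs. Each level holds only part of the sample, so its test has far less power than the whole-trial test. Under a uniform effect, some levels will miss 0.05 by chance.

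The stated aim of these analyses is to support the robustness of the primary result. The question a reader brings to them is whether the effect is consistent across kinds of patient. The plan produces a p-value for every level but none for that question. At stake is a false impression that the drug fails in, say, one sex or one DLCO group. The main error here is a false negative within a level, not a false positive.

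**Working it through.** **Inputs from SAP Section 5.** The plan is to "detect a 30 meter between-treatment difference", "assuming a standard deviation of 75 meters", at two-sided 0.05 with 1:1 allocation. It states that "approximately 266 subjects (133 per treatment) would provide at least 90% power", with about 314 in total (157 per arm) after allowing for 15% discontinuation.

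**The plan's own figure.** n per arm = 2 × (1.960 + 1.282)² × (75/30)² = 131.4, so 132. The exact t-test needs 133, with power 90.1%. Then 266/0.85 = 313, against 314 stated. The sample size reproduces.

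**Number of levels.** In the order etiology, walk at 350 m, walk at median, DLCO, sex, PVR, age, dose:
- Section 8.2: 6+2+2+2+2+2+3+4 = 23.
- Section 10.1.1.3: 5+2+2+2+2+2+3+4 = 22.

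**Power within a level.** For a level with m per arm, the noncentrality is 30/(75 × √(2/m)). For half of 133, m = 66.5, this is 0.4 × √33.25 = 2.31, and t-test power is 63%.

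**Chance that exactly one of two levels is significant.** With powers a and b in the two levels, this is a(1−b) + b(1−a). For an even split at 133 per arm: 2 × 0.629 × 0.371 = 0.467. The documents give no subgroup shares, so a range of splits is assumed:

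| Split | Powers, 133 per arm | One level only | Powers, 157 per arm | One level only |
|---|---|---|---|---|
| 50:50 | 63%, 63% | 47% | 70%, 70% | 42% |
| 70:30 | 77%, 42% | 54% | 84%, 48% | 51% |
| 80:20 | 83%, 30% | 63% | 88%, 34% | 62% |

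Both sample sizes matter. The design power rests on 133 per arm. The efficacy analyses use all randomized and dosed subjects with missing walks imputed (Sections 6 and 8.3.1), which is closer to 157.

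In factors with more levels, power is lower still: about 47% to 53% in a third of the sample and 26% to 30% in a sixth.

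**At least one of the five two-level factors.** The simple product, 1 − (1 − 0.467)⁵ = 96%, is too high because all five factors cut the same patients. Simulation with a uniform 30 m effect, SD 75 m, unadjusted t-tests and independently assigned factors gives:
- 133 per arm: about 80% at 50:50 and 91% at 70:30.
- 157 per arm: about 75% at 50:50 and 89% at 70:30.

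Across runs, with and without restriction to trials whose primary test is significant, the range is 74% to 93%.

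**With an interaction test instead.** Each test has a 5% false-signal rate under a uniform effect. Treating the tests as independent, the chance of at least one false signal is 1 − 0.95⁵ = 23% over the five two-level factors and 1 − 0.95⁷ = 30% over all seven baseline splits.

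**Power of the interaction test.** For an even split at 133 per arm, each half has SE 75 × √(2/66.5) = 13.0 m, so the difference between halves has SE 13.0 × √2 = 18.4 m. Power of 90% needs a true difference of (1.960 + 1.282) × 18.4 = 60 m, twice the planned overall effect.

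**The case against.** A reader might infer that the SAP judges subgroups by within-level significance. It does not: no section sets a decision rule or ties a claim to a subgroup p-value.

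A reader might also infer that nothing in the plan could correct a misreading. That goes too far. Subgroup differences with standard errors and 95% confidence intervals follow from repeating the primary analysis, and a forest plot is listed. Someone who knows the pitfall could form an approximate between-level contrast from these outputs. What stands is that the plan still prints a p-value per level and leaves the comparison to the reader.

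A third inference is that the trial's error control is at risk. For 23 independent tests the chance of a false positive is 1 − 0.95²³ = 69%, but that applies only if there is no effect at all. Under Section 10.1.1.3 these analyses follow a significant primary result, and they feed neither the primary test nor the fixed-sequence secondary tests.

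The word stratified could mean one pooled stratified test per factor. The section title, the separate tables by factor and the subgroup forest plot favor results by level. If pooling was meant, the text needs clarifying, and a between-level test is still absent.

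Finally, the two baseline-walk cuts divide the same variable, so the five factors are not independent. Letting those two overlap in the simulation lowered the result only slightly.

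**Conclusion.** The point holds as a gap in the exploratory analyses. The plan repeats the treatment test within 22 or 23 levels and includes no test of whether the effect differs between them. Under a uniform 30 m effect with SD 75 m, a two-level factor shows significance in one level only with probability 47% to 63% at 133 per arm and 42% to 62% at 157 per arm. The chance of at least one such factor among five is about 74% to 93%.

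These figures assume the splits shown, independent factors and t-tests without baseline adjustment. Adjustment for Baseline 6MWD could reduce the residual SD, and imputing 0 m could raise it, so the exact values will move. Across the splits and sample sizes tried, one-level-only significance remained common.

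The change is worth making before unblinding, but it concerns interpretation and reporting only. The primary and secondary conclusions and their Type 1 error stand.

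**What to change.** For each baseline factor, prespecify as exploratory one ANCOVA of change in peak 6MWD at Week 16 on treatment, Baseline 6MWD, subgroup and treatment-by-subgroup. Print the interaction p-value on the forest plot beside the planned estimates and 95% confidence intervals, and drop the within-level p-values. State which form the interaction analysis takes if the rank-based method replaces ANCOVA as primary.

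Report Week 16 dose descriptively, with no interaction test and no causal reading, because dose reached is an outcome of treatment and tolerance.

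Reconcile the etiology lists in Sections 8.2 and 10.1.1.3 on connective tissue disease, and say that the factor analyses give results by level, if that is the intent.

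The cost is a short SAP edit and one model per factor, with no new data. The downside is low power: a non-significant interaction does not prove consistency. Unadjusted tests over five to seven baseline factors also still carry about a 23% to 30% chance of at least one false signal, so the exploratory label and the intervals must stay beside the p-values.

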### **10.3 EXPLORATORY EFFICACY MEASURES**

Exploratory efficacy endpoints include the following parameters:

- Change in peak 6MWD from Baseline to Week 4
- Change in peak 6MWD from Baseline to Week 8
- Change in quality of life as measured by SGRQ from Baseline to Week 16
- Time to clinical worsening will be evaluated as an exploratory endpoint from the time to randomization until 1 of the following criteria are met:
  - a. Hospitalization due to a cardiopulmonary indication
  - b. Decrease in 6MWD >15% from Baseline directly related to disease under study, at 2 consecutive visits and at least 24 hours apart
  - c. Death (all causes)
  - d. Lung transplantation
- Change in DSP from Baseline to Week 16

# 10.3.1 Change in Peak 6MWD at Weeks 4 and 8

The methodology for primary efficacy analysis of change in peak 6MWD described in Section 10.1.1.2 will also be carried out for the assessments obtained at Week 4 and Week 8.

# 10.3.2 Change in SGRQ at Week 16

The responses to the SGRQ questionnaire at Baseline and Week 16 will be converted to the Total score and 3 domain scores according to the SGRQ manual (Jones 2002). Scores for Total and each domain will range from 0 to 100, with higher scores indicating more limitations. Both individual item responses as well as calculated scores will be listed. The change from Baseline for the Total and 3 domain scores (Symptoms, Activity, and Impacts) will be calculated.

The Total score and for the 3 domain scores as well as their changes from Baseline will be summarized by treatment group using descriptive statistics.

For the Total score and each of the 3 domain scores, treatment differences (inhaled treprostinil vs. placebo) will be tested by using analysis of covariance with change from Baseline as the dependent variable, treatment as a fixed effect, and baseline score as the covariate. The analyses will be based on the observed data with no imputation.

The pseudo SAS code is as follows:

proc glm; class treatment; model Score\_C=Treatment Score\_B; run;

where Score\_C is the change from Baseline in Total score or each of the 3 domain scores and Score\_B is the corresponding score at Baseline.

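### The supportive MMRM holds one Baseline 6MWD slope across Weeks 4 to 16; a Baseline-by-week term costs almost nothing and protects the Week 16 estimate if that slope changes

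*SAP*

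**What the plan says.** SAP 10.1.1.3 adds a longitudinal analysis of peak 6MWD to the sensitivity analyses. Change from Baseline is the response. The mean model has treatment, week and "treatment by week interaction as fixed effects, and Baseline 6MWD as a covariate". The within-subject covariance is unstructured and common to both arms. No product of Baseline and week is listed, and SAP 8.1 says only that the baseline measure will be the covariate. Peak walks are scheduled at Weeks 4, 8, 12 and 16 (protocol 3.3.1.1.3.1), so one slope covers four visits.

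The primary analysis (SAP 10.1.1.2) is an ANCOVA on the Week 16 change alone, with treatment and Baseline 6MWD in the model. Its Baseline slope is therefore specific to Week 16.

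**The concern.** An MMRM with treatment by week and an unstructured covariance leaves the treatment effect and the covariance free at each visit. Holding the Baseline slope constant is its one remaining restriction across visits. If the true slope differs by visit, the fitted slope is a weighted average that leans toward the less variable visits, often the early ones. Week 16, the visit of interest, is then adjusted with the wrong slope, and part of the Baseline variation stays in the error.

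Two things are at stake. One is the precision of the MMRM's Week 16 difference. The other is its use as a comparator: if it departs from the primary ANCOVA, a reader will want to attribute the gap to the handling of missing walks, and a misfitting covariate is a second, avoidable explanation. When missingness is related to Baseline, that misfit can also move the estimate.

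**Working it through.** **The plan's own figure.** SAP 5 states that "a sample size of approximately 266 subjects (133 per treatment) would provide at least 90% power". Its inputs are a two-sided 0.05 level, a difference of 30 m and an SD of 75 m. Normal approximation: n per arm = 2 × (1.960 + 1.282)² × 75² / 30² = 131.3, so 132. The noncentral t gives power 0.8993 at 132 and 0.9015 at 133 per arm, so 133 is reproduced. For discontinuation, 266 / 0.85 = 312.9, so 313, or 314 when made even. This is a two-sample calculation, and the MMRM plays no part in it.

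**Model.** Let the true slope at visit j be b_j, the Baseline SD be S, the residual SD at Week 16 be s, and the residual covariance be Σ. Under 1:1 randomization, with complete data and large samples:

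- Common slope: bc = (1′Σ⁻¹b) / (1′Σ⁻¹1)
- Variance of the Week 16 difference, common slope: (2/n) × [s² + (b16 − bc)² S²]
- Same, with Baseline by week: (2/n) × s²
- Variance reduction from the extra term: m / (s² + m), where m = (b16 − bc)² S²

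**Inputs.** The documents give no Baseline SD, visit-specific slopes, visit-specific SDs or between-visit correlations, so these are assumptions. Here S = 95 m (S² = 9025), s = 72 m (s² = 5184), and slopes change linearly over the four visits. The residual SD is either 72 m throughout or rises from 50 to 72 m.

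| Slope, Week 4 to Week 16 | Residual SD | bc | m | Variance reduction |
|---|---|---|---|---|
| −0.10 to −0.10 | either | −0.100 | 0 | 0% |
| −0.10 to −0.20 | constant | −0.150 | 0.050² × 9025 = 22.6 | 22.6/5206.6 = 0.4% |
| −0.10 to −0.20 | rising | −0.1008 | 0.0992² × 9025 = 88.8 | 88.8/5272.8 = 1.7% |
| −0.05 to −0.20 | constant | −0.125 | 0.075² × 9025 = 50.8 | 50.8/5234.8 = 1.0% |
| −0.05 to −0.20 | rising | −0.0512 | 0.1488² × 9025 = 199.8 | 199.8/5383.8 = 3.7% |
| −0.05 to −0.35 | constant | −0.200 | 0.150² × 9025 = 203.1 | 203.1/5387.1 = 3.8% |
| −0.05 to −0.35 | rising | −0.0525 | 0.2975² × 9025 = 798.8 | 798.8/5982.8 = 13.4% |

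The rising-SD rows use exchangeable correlation 0.7. Exchangeable 0.5 gives 1.1%, 2.4% and 8.8% for the three drifts, and AR(1) 0.8 gives 1.2%, 2.6% and 9.8%. Exchangeable 0.8 gives 2.5%, 5.4% and 18.6%. With constant SD the correlation makes no difference in these cases.

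**Range over the Baseline SD.** With Baseline SD 75 to 120 m, total SD of change 75 m at Week 16 (constant, or rising from 50 m), and correlation 0.7 exchangeable or 0.8 AR(1), the common slope inflates the standard error as follows:

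- Mild drift (−0.05 to −0.15): 0.1 to 1.4%
- Moderate drift (0 to −0.15): 0.3 to 3.1%
- Strong drift (0 to −0.30): 0.9 to 11.7%

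The top value checks by hand: s² = 75² − 0.30² × 120² = 4329, bc = −0.027, m = 0.273² × 14400 = 1073, and √(5402/4329) = 1.117.

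**Simulation** (N = 314, 500 to 600 replicates per setting, rising SD, Baseline SD 100 m). With complete data the ratio of model standard errors, common slope to Baseline by week, was 1.019 for moderate and 1.076 for strong drift. With about 13 to 14% missing at Week 16 it was 1.014 to 1.025 and 1.070 to 1.092.

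**Shift in the estimate** (true difference 30 m). With dropout related to Baseline and to the prior walk in the same way in both arms, the shift was 0.3 to 0.6 m. With dropout related to Baseline in opposite directions by arm, a deliberately extreme case, the common slope averaged 33.6 m (moderate drift) and 36.4 m (strong drift). Baseline by week averaged about 30.5 m in both.

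**Cost of the term when slopes are equal.** The model standard error rose from 8.367 to 8.375 m with complete data (0.008/8.367 = 0.1%), and by up to about 0.5% in the least favourable dropout setting tried.

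**The case against.** A single Baseline covariate with an unstructured covariance is a coherent, pre-specified model. Nothing in the documents says that the dependence of change on Baseline varies over visits. The larger gains need strong drift within 12 weeks, residual variance that rises over visits, or both. The observed-case, LOCF and LRCF sensitivity analyses already work on Week 16 alone. All of this stands. It makes the benefit conditional and usually small, but it does not argue for keeping the restriction, since relaxing it costs so little.

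The MMRM's role as a missing-data check is also not fully pinned down. SAP 10.1.1.3 opens by imputing missing walks under 8.3.1 and does not say whether the MMRM uses unimputed values. If imputed values enter, the model is not a likelihood-based check on missing data. Zeros alone would then matter little to this point: with 6% or 12% of Week 16 values set to 0 m and otherwise equal slopes, the standard-error ratio was 1.000 to 1.004.

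Four stronger readings are tempting, and the documents do not support them:

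- A reader might infer that the trial loses power. The primary ANCOVA already has its own Week 16 slope, the hierarchy in SAP 8.4 does not include the MMRM, and the sample size does not rest on it.
- A reader might infer that precision is certainly lost. With equal slopes nothing is lost.
- A reader might infer that the extra term is free. It spends three parameters.
- A reader might take SAP 10.3.1 as a second instance. There the single-visit primary methodology "will also be carried out for the assessments obtained at Week 4 and Week 8", with no repeated-measures model, so each visit fits its own slope.

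**Conclusion.** The point holds as a conditional, minor improvement. The MMRM as written imposes one Baseline slope on four visits. If the slopes are equal, that restriction is harmless. If they drift, the variance of the MMRM's Week 16 difference would be about 0.4 to 4% lower with visit-specific slopes under mild to moderate drift, and about 4 to 13% lower under strong drift. These figures assume a Baseline SD of 95 m, a Week 16 residual SD of 72 m and correlations up to 0.7; an exchangeable correlation of 0.8 with rising variance would take the two upper ends to about 5% and 19%. A shift in the estimate also needs Baseline-related missingness. It stayed under 1 m when dropout acted alike in both arms, and reached 3.6 to 6.4 m only in the extreme opposite-direction case. None of these inputs is in the documents, so the size cannot be fixed from them. No confirmatory conclusion depends on this term.

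**What to change.** In SAP 10.1.1.3, state the MMRM fixed effects as treatment, week, treatment by week, Baseline 6MWD, and Baseline 6MWD by week. Keep the unstructured covariance shared across arms. Make the change before unblinding so that it is not a post hoc choice.

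The cost is one term in one model statement and three more parameters, about 0.1% of the standard error and at most about 0.5% in the settings tried. Nothing else in the plan needs to change.
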